16.2. Close-out of a Site

The sponsor and the investigator have the right to close out a site prematurely.

Investigator's Decision

The investigator must notify the sponsor of a desire to close out a site in writing, providing at least 30 days' notice. The final decision should be made through mutual agreement with the sponsor. Both parties will arrange the close out procedures after review and consultation.

Sponsor's Decision

The sponsor will notify the investigator(s) of a decision to close out a study site in writing. Reasons may include the following, among others:

- The investigator has received all items and information necessary to perform the study, but has not enrolled any patient within a reasonable period of time
- The investigator has violated any fundamental obligation in the study agreement, including but not limited to, breach of this protocol (and any applicable amendments), breach of the applicable laws and regulations, or breach of any applicable ICH guidelines
- The total number of patients required for the study are enrolled earlier than expected

In all cases, the appropriate IRB/EC and Health Authorities must be informed according to applicable regulatory requirements, and adequate consideration must be given to the protection of the patients' interests.

17. STUDY DOCUMENTATION

17.1. Certification of Accuracy of Data

A declaration assuring the accuracy and content of the data recorded on the eCRF must be signed electronically by the investigator. This signed declaration accompanies each set of patient final eCRF that will be provided to the sponsor.

17.2. Retention of Records

The investigator must retain all essential study documents, including ICFs, source documents, investigator copies of CRFs, and drug accountability records for at least 15 years following the completion or discontinuation of the study, or longer, if a longer period is required by relevant regulatory authorities. The investigator must consult with the sponsor before discarding or destroying any essential study documents following study completion or discontinuation. Records must be destroyed in a manner that ensures confidentiality.

If the investigator's personal situation is such that archiving can no longer be ensured, the investigator must inform the sponsor and the relevant records will be transferred to a mutually agreed-upon destination.

18. CONFIDENTIALITY

Confidentiality of information is provided as a separate agreement.

19. FINANCING AND INSURANCE

Financing and insurance information is provided as a separate agreement.

20. PUBLICATION POLICY

The publication policy is provided as a separate agreement.

APPENDIX 1. KNOWN LPL AND APOC2 NULL (TOTAL LOSS OF FUNCTION) MUTATIONS

This list of LPL and APOC2 mutations is not comprehensive and is for reference only. Inclusion in the study is not limited to mutations in this list.

LPL	Variant	HGVS Nomenclature	Nucleotide Change	State	Reference
1	1	Met-27Ile	M1I	3G>C	Homozygous
2	1	Trp-14Ter	W14X	42G>A	Homozygous
3	1	pQ-12E>11X	46_47del2	Compound Heterozygous	Wang J 2007
4	Intron	IVS1+1G>C		Homozygous	Chimienti G 1992
5	Intron	89-4_89-2del3		Compound Heterozygous	Hölzl B 2000
6	2	133_143del11		Compound Heterozygous	Reina M 1992
7	2	Cys27Ter	C54X	162C>A	Compound Heterozygous
8	2	183dup1		Homozygous	Benlian P AJHG 1996
9	2	Asn43Ser	N70S	209A>G	Homozygous
10	Intron	IVS2+1G>A		Homozygous	Gotoda T 1991
11	Intron	IVS2-1G>A		Compound Heterozygous	Hata A 1990
12	3	Tyr61Ter	Y88X	264T>A	Homozygous
13	3	Trp64Ter	W91X	272G>A	Compound Heterozygous
14	3	287_288del2		Compound Heterozygous	Foubert L 1998
15	3	290_293del4ins2		Compound Heterozygous	Benlian P 1996
16	3	Tyr73Ter	Y100X	300A>C	Compound Heterozygous
17	3	Arg75Ser	R102S	306A>C	Compound Heterozygous
18	3	Trp86Arg	W113R	337T>C	Compound Heterozygous
19	3	384del1ins6		Homozygous	Henderson HE 1990

	LPL	Variant	HGVS Nomenclature	Nucleotide Change	State	Reference
20	3	Gly105Arg	G132R	394G>A	Compound Heterozygous	Ikeda Y 2000
21	3	Gln106Ter	Q133X	397c>t	Homozygous	Emi M AJHG 1990
22	4	440_443del4			Compound Heterozygous	Ma Y 1993
24	4	Gly139Ser	G166S	496G>A	Homozygous	Bijvoet S 1994
25	4	Gly142Glu	G169E	506G>A	Homozygous	Ameis D 1991
26	4	Gly154Ser	G181S	541G>A	Homozygous	Bruin T JLR 1993
27	5	Gly154Val	G181V	542G>T	Compound Heterozygous	Ikeda Y 2001
28	5	Asp156Asn	D183N	547G>A	Compound Heterozygous	Ma Y 1992
29	5	Asp156Gly	D183G	548A>G	Homozygous and Compound Heterozygous	Ma Y 1992, Faustinella F 1991
30	5	Pro157Arg	P184R	551C>G	Homozygous	Bruin T 1992
31	5	Ala158Thr	A185T	553G>A	Homozygous	Mailly F 1997
32	5	Ala176Thr	A203T	607G>A	Homozygous	Beg OU 1990
33	5	Asp180Glu	D207E	621C>G	Homozygous	Haubenwallner S 1993
34	5	His183Asp	H210D	628C>G	Compound Heterozygous	Hölzl B 2000
35	5	Gly188Arg	G215R	643G>A	Homozygous	Benlian P 1996
36	5	Gly188Glu	G215E	644G>A	Homozygous	Emi M JBC 1990, Monsalve MV 1990
37	5	Arg192Ter	R219X	655C>T	Homozygous	Zhang Q 1997
38	5	Ser193Arg	S220R	658A>C	Compound Heterozygous	Mailly F 1997
39	5	Ile194Thr	I221T	662T>C	Homozygous	Henderson HE 1991
40	5	Gly195Glu	G222E	665G>A	Homozygous	Hata A 1992
41	5	Asp204Glu	D231E	693C>G	Homozygous	Gotoda T 1991
42	5	Ile205Ser	I232S	695T>G	Homozygous	Reina M 1992
43	5	Pro207Leu	P234L	701C>T	Homozygous and Compound Heterozygous	Ma Y 1991, Yang Y 2007
44	5	Cys216Ser	C243S	727T>A	Compound Heterozygous	Ma Y 1992

LPL	Variant	HGVS Nomenclature	Nucleotide Change	State	Reference
45	5	742del1		Homozygous	Takagi A 1992
46	5	Ile225Thr	I252T	755T>C Compound Heterozygous	Henderson HE 1993
47	6	Cys239Ter	C266X	798C>A Homozygous	Takagi A 1994
48	6	Cys239Trp	C266W	798C>G Homozygous	Hoffmann MM 2000
49	6	Arg243His	R270H	809G>A Homozygous and Compound Heterozygous	Gotoda T 1991, Dichek HL 1991
50	6	Ser244Thr	S271T	811T>A Compound Heterozygous	Hata A 1990
51	6	Asp250Asn	D277N	829G>A Homozygous	Ma Y 1992
52	6	835_836del2		Homozygous	Mailly F 1997
53	6	Ser251Cys	S278C	833C>G Compound Heterozygous	Bijvoet SM 1996
54	6	Leu252Val	L279V	835C>G Compound Heterozygous	Chan L 2000
55	6	Leu252Arg	L279R	836T>G Compound Heterozygous	Chan L 2000, Ma Y 1994
56	6	Ser259Arg	S286R	858T>A Homozygous	Foubert L 1997
57	6	Tyr262His	Y289H	865T>C Homozygous	Rouis M 1996
58	6	Cys264Tyr	C291Y	872G>A Homozygous	Murugasu CG 1998
59	6	Phe270Leu	F297L	891T>G Homozygous	Takagi A 2000
60	6	Leu276Phe	L303F	909G>C Homozygous	Saika Y 2003
61	6	Leu286Pro	L313P	938T>C Compound Heterozygous	Benlian P 1996
62	6	Tyr288Ter	Y315X	945T>A Homozygous	Causeret AS 2001
63	6	953del1		Compound Heterozygous	Kobayashi J 1999
64	6	Tyr302Ter	Y329X	987C>A Homozygous	Bertolini S 2000
65	Intron	IVS6-3C>A		Homozygous and Compound Heterozygous	Hölzl B 1994
66	8	Trp382Ter	W409X	1227G>A Homozygous	Gotoda T 1991
67	8	1227del1		Homozygous	Gotoda T 1991, Maruyama T 2004
68	8	1314_1315del2		Homozygous	Nierman MC 2006

	LPL	Variant	HGVS Nomenclature	Nucleotide Change	State	Reference
69	Intron	IVS8+2T>C			Compound Heterozygous	Ikeda Y 2001

LPL	Variant	HGVS Nomenclature		Nucleotide Change	State	Reference		
		APOC2	Exon	Variant/HGVS-Nomenclature	Nucleotide Change	Mutation Type	State	Reference
1	Prom			7.5 kb promoter + ex. 1 Deletion		Gross Deletion	Homozygous	Fu J 2013
2	Prom			-25 relative to transcription initiation site		Regulatory	Homozygous	
3	1			M1V	1A>G	Missense	Homozygous	
4	1			R4X	10C>T	Nonsense	Homozygous	
5	Intron			55+1G>C	55+1G>C	Splicing	Homozygous	
6	2			70delC		Small Deletion	Homozygous	
7	2			118delG		Small Deletion	Homozygous	
8	2			K41T	122A>C	Missense	Homozygous	
9	2			W48R	142T>C	Missense	Homozygous	
10	2			Y59X	177C>A	Nonsense	Homozygous	
11	2			E60K	178G>A	Missense	Homozygous	
12	3			Y85X	255C>A	Nonsense	Homozygous	

10.4.1.	Footnotes for the Schedule of Events Table	61

LIST OF TABLES

Table 1: Schedule of Events	57
-----------------------------------	----

LIST OF FIGURES

Figure 1: Study Flow Diagram.....	16
-----------------------------------	----

LIST OF ABBREVIATIONS AND DEFINITION OF TERMS

ADA	Anti-drug antibody
ADC	Apparent diffusion coefficient
AE	Adverse event
AESI	Adverse event of special interest
ALT	Alanine aminotransferase
ANGPTL3	Angiopoietin-like 3
APO	Apolipoprotein
AP	Acute pancreatitis
AST	Aspartate aminotransferase
BUN	Blood urea nitrogen
CABG	Coronary Artery Bypass Grafting
CI	Confidence interval
CM	Chylomicrons
CPK	Creatine phosphokinase
CRF	Case report form (electronic or paper)
CV	Cardiovascular
CVD	Cardiovascular disease
DBTP	Double-blind treatment period
DW-MRI	Diffusion Weighted-Magnetic Resonance Imaging
ECG	Electrocardiogram
EOT	End of treatment
FAS	Full analysis set
FCS	Familial Chylomicronemia Syndrome
FFA	Free fatty acids
¹⁸ F-FDG PET	¹⁸ F-2-Fluoro-2-Deoxy-D glucose positron emission tomography
FSH	Follicle stimulating hormone
GI	Gastrointestinal
HbA1c	Hemoglobin A1c
HDL	High-density lipoprotein
HDL-C	High-density lipoprotein cholesterol
HL	Hepatic lipase
HTG	Hypertriglyceridemia
ICH	International Council for Harmonization
ICF	Informed consent form

IDMC	Independent Data Monitoring Committee
IV	Intravenously
IVRS	Interactive voice response system
Ki	Incorporation rate
Kpatlak	Patlak clearance rate
LDH	Lactate dehydrogenase
LDL-C	Low-density lipoprotein cholesterol
LDLR	Low-density lipoprotein receptor
LOF	Loss of function
Lp(a)	Lipoprotein a
LPL	Lipoprotein lipase
LS	Least squares
MedDRA	Medical Dictionary for Regulatory Activities
MMRM	Mixed-effect model with repeated measures
MRI	Magnetic resonance imaging
NMR	Nuclear Magnetic Resonance
PCI	Percutaneous Coronary Interventions
PCSV	Potentially clinically significant value
PET	Positron emission tomography
PK	Pharmacokinetic
PRO	Patient-Reported Outcomes
PT	Preferred term
Q4W	Every 4 weeks
RBC	Red blood cell
Regeneron	Regeneron Pharmaceuticals, Inc.
SAE	Serious adverse event
SAF	Safety analysis set
SAP	Statistical analysis plan
SAS	Statistical Analysis System
SBTP	Single-blind treatment period
SD	Standard deviation
SE	Standard error
sHTG	Severe hypertriglyceridemia
SOC	System organ class
TBR	Target to background ratio
TC	Total cholesterol
TEAE	Treatment-emergent adverse event

TG	Triglycerides
TSH	Thyroid stimulating hormone
ULN	Upper limit of normal
VLDL	Very-low-density lipoproteins
WBC	White blood cell

1. OVERVIEW

The purpose of the statistical analysis plan (SAP) is to ensure the credibility of the study results by pre-specifying prior to the database lock the statistical approaches for the analysis of study data. The SAP is intended to be a comprehensive and detailed description of the strategy and statistical methods to be used in the analysis of data collected in the R1500-HTG-1522 study. The content of this SAP is inclusive of the interim, first, and second step analyses as described in the protocol.

This plan may be revised during the study to accommodate protocol amendments and adapt to unexpected issues in study execution that may affect planned analyses. These revisions will be based on blinded data review, and a final plan will be issued prior to the first interim database lock (i.e. before any treatment assignments become known). For the purposes of this document, REGN1500 will be referred to as “evinacumab”.

1.1. Background/Rationale

Elevated levels of serum triglycerides (TG) are associated with the development of cardiovascular disease (CVD) and acute pancreatitis (AP). Studies suggest that mild to moderate elevations in TG levels are an independent risk factor for the development of CVD, and recent studies have demonstrated that genetic loss of function (LOF) variants which result in lower TG levels (eg, apolipoprotein C3 (APOC3), ANGPTL3, and ANGPTL4 LOF genetic variants) are associated with a decreased risk of myocardial infarction. Patients with severe elevations in TG levels (>1000 mg/dL) are at increased risk of pancreatitis and current lipid guidelines recommend lifestyle interventions and medications to lower TG levels to prevent AP.

Angiopoietin-like 3 is the natural inhibitor of lipoprotein lipase (LPL) and has recently emerged as a potential target for the treatment of elevated levels of TG, and low-density lipoprotein cholesterol (LDL-C). Loss of function of ANGPTL3 in humans has been associated with reductions in TG, LDL-C and high-density lipoprotein-cholesterol (HDL-C). Deficiency of ANGPTL3 has also been reported to be associated with decreased serum free fatty acids (FFA) and increased insulin sensitivity in patients who are homozygous for LOF mutations in ANGPTL3. Humans carrying these variants have otherwise appeared healthy and have a reduced risk of coronary artery disease.

Evinacumab (REGN1500) is a human IgG4 monoclonal antibody specific for ANGPTL3 and is being developed for treatment of dyslipidemia including hypertriglyceridemia (HTG) and hypercholesterolemia. Additional background information on the study drug and development program can be found in the Investigator’s Brochure.

1.2. Study Objectives

1.2.1. Primary Objectives

The primary objective of the study is to determine the change in TG levels following 12 weeks of repeated IV doses of evinacumab in the subset of patients with a documented history of sHTG (TG \geq 1000 mg/dL [11.3 mmol/L]), a TG level of at least 500 mg/dL (5.6 mmol/L) at screening, a history of acute pancreatitis and without LOF mutations in genes in the LPL pathway; and to assess whether a reduction in TG of at least 40% from the baseline placebo period has been achieved.

Regeneron and contract research organization (CRO) personnel who are in regular contact with the study site will be blinded to blood lipid measurements during the double-blind and single-blind treatment periods

1.2.2. Secondary Objectives

The secondary objectives of the study are:

- To determine the percent change from baseline in TG levels following 2 to 24 weeks of repeated IV doses of evinacumab overall and in subgroups with homozygous or compound heterozygous LOF mutations, heterozygous LOF mutations, and without LOF mutations in genes in the LPL pathway
- To assess changes in patient reported abdominal and gastrointestinal (GI) symptoms, dietary habits, and symptom/dietary impact measures
- To assess the degree of pancreatic injury/inflammation through 18F-2-Fluoro-2-Deoxy-D glucose positron emission tomography (18F-FDG-PET) imaging at baseline (placebo run-in) and change from baseline following 12 weeks of treatment with evinacumab as assessed by 18F-FDG standardized uptake values SUVmax and SUVmean
- To assess the degree of pancreatic injury/inflammation through diffusion weighted-magnetic resonance imaging (DW-MRI) at baseline and the change from baseline following 12 and 24 weeks of treatment with evinacumab as assessed by apparent diffusion coefficient (ADC)
- To evaluate the total evinacumab and total ANGPTL3 concentrations, and treatment-emergent anti-drug antibody (ADA) incidence during the evinacumab treatment and follow-up periods
- To evaluate the safety and tolerability of evinacumab

1.2.3. Exploratory Objectives

- To assess the degree of pancreatic injury/inflammation in the placebo run-in period and following treatment with evinacumab, as assessed by biochemical markers (amylase and pancreatic lipase activity [measured without lipemia interference], hs-CRP, IL-6, and other inflammation markers)

- To evaluate the effect of evinacumab compared to placebo on the incidence of recurrent acute pancreatitis overall and in subgroups with homozygous or compound heterozygous LOF mutations, heterozygous LOF mutations, and without LOF mutations in genes in the LPL pathway
- To assess hospitalizations for abdominal pain, hospitalizations for pancreatitis, and hospitalizations for cardiovascular disease
- To assess the degree of pancreatic injury/inflammation through T2-weighted magnetic resonance imaging (T2-MRI) at baseline and the change from baseline following 12 and 24 weeks of treatment with evinacumab as assessed by T2 intensity and T2 relaxation time
- To assess the degree of pancreatic injury/inflammation through 18F-2-Fluoro-2-Deoxy-D glucose positron emission tomography (18F-FDG-PET) imaging at baseline (placebo run-in) and change from baseline following 12 weeks of treatment with evinacumab as assessed by 18F-FDG Ki or Kpatlak
- To evaluate the percent change from baseline of other lipid parameters (eg, total cholesterol [TC], TG, non-HDL-C, LDL-C, HDL-C, APOB, FFA, APOA-I) and lipoprotein subfraction composition (eg, chylomicrons [CM], VLDL, IDL, LDL [low-density lipoprotein], HDL [high-density lipoprotein], particle cholesterol, TG content, and apolipoprotein composition) after ultracentrifugation
- To evaluate change from baseline in metabolic parameters (fasting blood glucose, insulin, C-peptide, HbA1c) after 12 and 24 weeks of evinacumab treatment
- To evaluate change from baseline in post heparin LPL activity after evinacumab treatment.
- To evaluate changes in 18F-FDG-PET in atherosclerotic plaque (target to background ratio [TBR]) in carotids and/or aorta
- To evaluate change from baseline in MRI liver fat signal
- To evaluate changes in the number and percentage of stomach pain, pain and abdominal symptom-free days, defined as the number and percentage of stomach pain free days, number of pain free days, and the number of abdominal symptom free days, as assessed by the HAP-SS.
- To evaluate changes in the number and percentage of days where meals are avoided as assessed by the HAP-DB.

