10.5. Interim Analysis

Interim analyses may be conducted during the course of the study by the unblinded team to assess efficacy, safety, and futility. If the timing of this analysis falls within a few weeks of the first-step analysis, only the first-step analysis will be performed. Enrollment (up to a maximum of approximately 50 patients) may be halted if the incidence of pancreatitis is much lower than anticipated, making the evaluation of a treatment effect on pancreatitis futile. Details of the interim analysis will be described in the SAP.

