2. INVESTIGATION PLAN

2.1. Study Design and Randomization

This is a phase 2, randomized, placebo-controlled, study designed to evaluate the efficacy and safety of repeated doses of evinacumab in adult patients with severe HTG. Up to approximately 50 patients will be enrolled, randomized 2:1 (evinacumab:placebo) to receive evinacumab 15 mg/kg IV every 4 weeks (Q4W) or matching placebo IV Q4W for the 12-week double-blind treatment period (DBTP). After completion of the DBTP, all patients will enter a 12-week single-blind treatment period (SBTP) and receive open-label evinacumab 15 mg/kg IV Q4W. Investigators, Regeneron Study Director, Medical Monitor, Study Monitor, and any other Regeneron and contract research organization (CRO) personnel who are in regular contact with the study site will be blinded to treatment assignment during the double-blind treatment period of

the study and blinded to blood lipid measurements during the double-blind and single-blind treatment periods. After SBTP, all patients will undergo a 24-week follow-up after the last dose of study treatment.

The following cohorts will be enrolled based upon information (or lack of information) on genotype in the patient's medical history at screening:

1. Cohort 1: FCS due to complete LPL deficiency. Approximately 6 to 9 patients will be enrolled. This cohort consists of patients:
 - with known homozygous or compound heterozygous null LPL, GPIHBP1, or APOC2 LOF mutations
2. Cohort 2: Multifactorial chylomicronemia with partial LPL deficiency. Approximately 9 to 12 patients will be enrolled. This cohort consists of patients:
 - with known heterozygous null LPL, GPIHBP1, or APOC2 LOF mutations, or
 - with uncharacterized or known non-null LOF LPL pathway gene mutations (LPL, apoC2, apoA5, LMF1 and GPIHBP1)
3. Cohort 3: Multifactorial chylomicronemia. Approximately 15 to 27 patients will be enrolled. This cohort consists of patients not included in cohorts 1 or 2 above:
 - with other monogenic or polygenic causes of sHTG (eg, CGKR, CREB3L3, E2/E2 dysbetalipoproteinemia), or
 - without genotype information

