2.2. Sample Size and Power Considerations

Percent change in TG is analyzed based on log (post/pre) transformation, allowing for a normal distribution of the data. Standard deviations (SD) of raw percent changes up to 13% are akin to moderate SD on the log scale (30-40%). For the statistical precision calculations, a log-scale SD of 0.5 was used based on available evinacumab phase 1 data and is assumed to be conservative. With N=10 patients, the 90% confidence interval (CI) for an estimated mean reduction in triglycerides of 40% is approximately 20% to 55%. With N=12, the CI is 22% to 54%. A sample size of 24 is considered adequate to analyze the percent change in TG in the 3 genetic cohorts. Assuming a 20% drop out rate, approximately 30 patients will be needed to assess TG. Additional patients (up to a maximum of approximately 50 patients) will be enrolled with the intent to explore the effect of evinacumab on development of pancreatitis.

For the FDG-PET uptake signal SUVmax, prior data on steroid-treated patients yielded a natural log-scale SD of change of 0.66 ([Shigekawa 2010](#)). This yields 80% power to yield a statistically significant ($\alpha=0.05$, 1-sided) change from baseline within the N=16 evinacumab-treated patients if the TRUE underlying geometric mean ratio (post/pre) is 0.65 (back-transformed from the log-scale; ~35% reduction). For comparison to the N=8 placebo-treated patients, assuming log-scale SD=0.15 for placebo based on reproducibility data, and 0.66 for evinacumab, there is 80% power if the TRUE underlying geometric mean ratio (GMR) of GMR's (evinacumab post/pre divided by placebo post/pre) is 0.64 (~36% reduction).

[figure not shown]
For the key MRI endpoint "mean f", which is the weighting coefficient between contrasting MRI regions (Klauss 2015), reported summary statistics yielded an SD estimate at most 5.96 for change from baseline. With this assumed SD, the N=24 patients with evinacumab post- and pre-values have 80% power to yield a statistically significant (alpha=0.05, 1-sided) change from baseline if the TRUE underlying mean change is 3.12 (~30% from baseline 10.5, which was observed by Klauss [Klauss 2015]). For the between-treatment comparison (N=16 evinacumab vs N=8 placebo), there is 80% power if the TRUE difference is 6.62 (~63% of the 10.5 baseline value observed by Klauss [Klauss 2015]).

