5.8. Analysis of Safety Data

The summary of safety results will be presented separately for the DBTP and SBTP, unless otherwise noted. Safety summaries for the DBTP will be presented by treatment groups (evinacumab, placebo), as well as by treatment group within each cohort containing patients from the double-blind safety analysis set. Safety summaries for the SBTP will be presented by all patients and by treatment group in DBTP (i.e., evinacumab, placebo), for patients in the single-blind safety analysis set. No formal inferential testing will be performed for either period. Summaries will be descriptive in nature.

General common rules

All safety analyses will be performed, unless otherwise specified, using the following common rules:

- Safety data in patients who do not belong to the safety analysis set (i.e., exposed but not randomized) will be listed separately.
- PCSV values are defined as abnormal values considered medically important by the Sponsor according to predefined criteria/thresholds based on literature review and defined by the Sponsor for clinical laboratory tests and vital signs (PCSV version dated January 2009 [[Appendix 10.3](#)]). Considering that the threshold defined in the PCSV list for monocytes and basophils can be below the ULN, the following PCSV criterion will be used for the PCSV analysis of monocytes and basophils:
 - PCSV criterion for monocytes: >0.7 Giga/L or $>\text{ULN}$ (if $\text{ULN} \geq 0.7$ Giga/L).
 - PCSV criterion for basophils: >0.1 Giga/L or $>\text{ULN}$ (if $\text{ULN} \geq 0.1$ Giga/L).
- PCSV criteria will determine which patients had at least 1 PCSV during the respective TEAE periods, taking into account all evaluations including unscheduled or repeated evaluations.
- For summary tables, only protocol scheduled measurements (as defined by e-CRF visit label) will be included. Patient listings will include all measurements, scheduled and unscheduled.
- The treatment-emergent PCSV denominator by treatment group for a given parameter will be based on the number of patients assessed for that given parameter at least once during the respective TEAE periods.
- For quantitative safety parameters including central laboratory measurements and vital sign scores, descriptive statistics will be used to summarize observed values and change from baseline values by visit.

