5.8.3. Analysis of Incidence of Recurrent Acute Pancreatitis

Acute pancreatitis event incidence table will present the number (n) and percentage (%) of patients experiencing such event. Multiple occurrences of the same event in the same patient will be counted only once in the tables within a treatment phase (TEAE or post-treatment AE). The denominator for computation of percentages is the respective safety analysis set within each treatment group.

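### The pancreatitis objective compares evinacumab with placebo and is the only stated reason for enrolling beyond about 30 patients, but SAP 5.8.3 plans per-arm counts and percentages with no between-arm difference or interval

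*SAP*

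**What the plan says.** The objective appears in Protocol 2.3 and SAP 1.2.3 as exploratory: "To evaluate the effect of evinacumab compared to placebo on the incidence of recurrent acute pancreatitis overall", and also by genotype subgroup.

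On numbers, Protocol 10.2 and SAP 2.2 agree. For TG: "A sample size of 24 is considered adequate to analyze the percent change in TG in the 3 genetic cohorts", and "Assuming a 20% drop out rate, approximately 30 patients will be needed to assess TG". Patients beyond that, up to about 50, "will be enrolled with the intent to explore the effect of evinacumab on development of pancreatitis". No other reason for them is given. Protocol 10.5 and SAP 7 also tie the stopping of enrolment to this outcome: it "may be halted if the incidence of pancreatitis is much lower than anticipated, making the evaluation of a treatment effect on pancreatitis futile".

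On analysis, SAP 5.8.3 says: "Acute pancreatitis event incidence table will present the number (n) and percentage (%) of patients experiencing such event". The denominator is the safety set of each arm. SAP 5.8 adds "No formal inferential testing will be performed for either period", calls the summaries descriptive, and provides double-blind safety tables by arm and by arm within cohort. Protocol 10.4.3.2 likewise assigns counts and percentages to binary endpoints.

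By contrast, SAP 5.11 plans a between-arm difference in PRO change scores, with a 95% CI if the data are normally distributed. The same paragraph excludes formal testing.

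**The concern.** The question is comparative, and up to 20 patients are recruited to address it, yet the specified output stops at two separate percentages. Only the 12-week double-blind period has a concurrent placebo arm; everyone who continues then receives evinacumab. That period is therefore the trial's only randomised evidence on pancreatitis.

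With few events, bare percentages can mislead in either direction: 0% versus 12% may be read as protection, and 6% versus 6% as absence of effect. Both directions matter here. Pancreatitis is also an adverse event of special interest, and Protocol 1 reports acute pancreatitis in 3 of 6 evinacumab patients and 1 placebo patient in an earlier cohort, judged unrelated to the drug.

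**Working it through.** **1. The plan's own figure.** 24 evaluable patients with 20% dropout: 24 / (1 - 0.20) = 30, as stated. The maximum of about 50 adds 50 - 30 = 20 patients, or 20/50 = 40% of maximum enrolment. No pancreatitis rate, effect size or precision is stated for them, so there is no pancreatitis figure to reproduce.

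**2. Arm sizes.** At 2:1 allocation (SAP 2.1), 50 × 2/3 ≈ 33 on evinacumab and 50 × 1/3 ≈ 17 on placebo.

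**3. What an interval would show.** Newcombe's method takes the Wilson limits (l, u) of each proportion. With d = p_E - p_P:

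- lower limit = d - √[(p_E - l_E)² + (u_P - p_P)²]
- upper limit = d + √[(u_E - p_E)² + (p_P - l_P)²]

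For 0/33 versus 2/17, the Wilson limits are 0 to 0.104 and 0.033 to 0.343, and d = 0 - 0.118 = -0.118.

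- lower limit = -0.118 - √[0² + (0.343 - 0.118)²] = -0.343
- upper limit = -0.118 + √[0.104² + (0.118 - 0.033)²] = +0.017

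The documents give no expected incidence, so all event counts below are assumptions.

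| Evinacumab | Placebo | Difference (points) | 95% CI |
|---|---|---|---|
| 0/33 | 2/17 | -11.8 | -34.3 to +1.7 |
| 1/33 | 2/17 | -8.7 | -31.4 to +6.2 |
| 2/33 | 3/17 | -11.6 | -35.4 to +6.2 |
| 2/33 | 1/17 | +0.2 | -21.4 to +14.6 |

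If enrolment stopped near 30 (20 versus 10), one event per arm would give -5.0 points (-35.7 to +15.3).

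**4. Does the choice of method matter?** For 0/33 versus 2/17, the simple Wald interval has SE = √(0.118 × 0.882 / 17) = 0.078. It gives -0.118 ± 1.96 × 0.078, or about -27 to +4 points, against -34 to +2 by Newcombe. The lower limit moves by 7 points on the same four counts.

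**5. The counting window.** SAP 5.8.3 counts events within the TEAE phase. Under SAP 4.8.1 the double-blind TEAE period ends the day before the first single-blind dose for patients who continue, nominally day 84. For patients who do not continue, it ends at last double-blind dose + 168 days. If the last dose was on day 57, that is day 57 + 168 = 225; if it was on day 1, day 1 + 168 = 169. So the window is two to nearly three times as long for non-continuers (169/84 = 2.0; 225/84 = 2.7). A difference computed on that count would mix unequal follow-up if discontinuation differed by arm.

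**The case against.** The strongest defence is that the omission is deliberate and consistent. The objective is exploratory, Protocol 10.1 plans no formal hypothesis test, and the SAP follows the protocol's rule for binary endpoints. This stands: a reader might infer that the SAP contradicts the protocol, and it does not. The gap lies between the objective and its analysis.

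A reader might also infer that the randomised period will yield no information on the effect. That goes too far. The arms are tabulated side by side with denominators, so the difference is one subtraction and an interval follows from the same four counts. What is missing is a prespecified estimate: the method and window would be chosen after the data are seen, whereas SAP 1 aims to fix the approach before database lock.

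The PRO comparison carries limited weight. Those scores are continuous, support a secondary objective, and have a conditional interval, so different handling of a sparse exploratory binary outcome is not in itself inconsistent. SAP 5.11 does show that this SAP regards a descriptive interval as compatible with a no-testing rule.

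Finally, an interval on the existing SAP 5.8.3 count could convey false precision because of the unequal windows. That is correct, and it shapes the fix.

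**Conclusion.** The point holds as an inexpensive improvement. A comparative exploratory objective, which alone justifies up to 20 of about 50 patients, has no planned between-arm estimate and no measure of uncertainty. In the illustrations at 33 versus 17, the 95% interval is about 36 to 42 points wide and includes zero each time, which bare percentages would not convey.

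These widths assume the event counts shown, full enrolment of about 50 (a ceiling, since enrolment may be halted earlier) and follow-up of every patient through the window.

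A reader might go on to infer that the trial is underpowered for pancreatitis or should test it. The documents do not support that as a defect: they claim no power for this outcome and state no expected incidence, and an exploratory aim can be met by estimation. The primary and secondary conclusions are unaffected.

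**What to change.** In SAP 5.8.3, add one descriptive row: the risk difference, evinacumab minus placebo, in patients with at least one acute pancreatitis event, with a 95% CI by a single named method (Newcombe or exact unconditional). Present it overall only, with no test.

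For this row, count events in both arms from the first double-blind dose to the earlier of the first single-blind dose or nominal week 12 (day 85). Do not use the double-blind TEAE period. Cohort-level results can stay as the counts already planned in SAP 5.8. SAP 2.2 needs no change.

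The cost is one paragraph of SAP text and one table row, with no new data. The downside is that the interval will be wide and will limit what can be said about pancreatitis in either direction.
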